¹ An Unscheduled Relapse Assessment Visit will be conducted within 72 hours of symptom onset of a suspected relapse (i.e., new or recurrent neurologic symptom[s]).

² Discontinuation refers to discontinuation of study treatment. Withdrawal refers to withdrawal of subjects from the study. The Discontinuation/Withdrawal Visit should be conducted as soon as possible and no later than 4 weeks after the last dose of study treatment.

CONFIDENTIAL

The information contained herein may not be used, disclosed, or published without the written consent of Biogen MA Inc.

³ Subjects who complete, temporarily withhold, or permanently discontinue study treatment for any reason and have a lymphocyte count <LLN will continue protocol-required visits and assessments and be followed every 4 weeks for 24 weeks and then every 3 months (**unless clinically indicated more often or at the Investigator's discretion**) until the lymphocyte count is \geq LLN or for 52 weeks after the last dose, or until one of the following occurs: 1) the subject continues on commercial BG00012 following study withdrawal/completion, or 2) the subject is initiated on another MS disease-modifying therapy. Note: lymphocyte counts \geq LLN at 2 consecutive visits are required.

⁴ Vital signs include body temperature, pulse rate, and systolic/diastolic blood pressure measurements.

⁵ Hematology testing must be performed every 4 weeks in subjects with lymphocyte count <LLN.

⁶ Study treatment must be temporarily withheld or permanently discontinued if any of the laboratory values meet the criteria defined in the protocol.

⁷ For females of childbearing potential.

⁸ Urine cytology must be performed if a subject experiences hematuria (of unknown etiology) at 2 consecutive visits or at the Unscheduled Relapse Assessment Visit or the Discontinuation/Withdrawal Visit.

⁹ An MRI must not be performed within 30 days of receiving a course of steroids.

¹⁰ A brain MRI scan will be performed unless assessed in the last 30 days.

CONFIDENTIAL

The information contained herein may not be used, disclosed, or published without the written consent of Biogen MA Inc.

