10. DISCONTINUATION OF STUDY TREATMENT AND/OR WITHDRAWAL OF SUBJECTS FROM THE STUDY

10.1. Discontinuation of Study Treatment

A subject *must* permanently discontinue BG00012 for any of the following reasons:

- The subject becomes pregnant. Study treatment must be discontinued immediately. Report the pregnancy according to the instructions in Section [15.4.1](#).
- The subject experiences a medical emergency that necessitates permanent discontinuation of study treatment.
- The subject has lymphocyte count $<500/\text{mm}^3$ for 6 months as outlined in [Table 4](#) and [Table 5](#).
- The subject experiences a protocol-specified change in laboratory values that necessitates permanent discontinuation of treatment as outlined in [Table 3](#) and [Table 4](#).
- The subject cannot tolerate study treatment.
- The subject receives any of the disallowed concomitant medications for this study.
- The subject or subject's parent/legal guardian desires to discontinue treatment.
- At the discretion of the Investigator for medical reasons or for noncompliance.

The reason for discontinuation of study treatment must be recorded in the subject's eCRF.

Subjects who discontinue treatment may remain in the study and continue protocol-required tests and assessments.

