16.5.1.2. Clinical Laboratory Results

Clinical laboratory evaluations including hematology, blood chemistry, and urinalysis will be summarized using the incidence of shifts outside the normal range. In addition, summary statistics for quantitative laboratory values and changes from baseline will be presented.

Lymphocyte count data will be summarized by timepoints on study treatment. Additionally, lymphocyte count over time post-treatment and the time to recovery will be descriptively summarized for subjects who develop decreases in lymphocyte count (<LLN).

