### 3 STUDY ACTIVITIES

**Table 1: Schedule of Activities for 109MS311**

Tests and Assessments 	Year 1						Year 2					Safety Follow-Up Visit
	Baseline Visit (Day 1) 	Visit 1 (Week 12±5d)	Visit 2 (Week 16 ±5d)	Visit 3 (Week 24 ±5d)	Visit 4 (Week 36 ±5d)	Visit 5 (Week 48 ±5d)	Visit 6 (Week 60 ±5d)	Visit 7 (Week 64 ±5d)	Visit 8 (Week 72 ±5d)	Visit 9 (Week 84 ±5d)	Visit 10 (Week 96 ±5d)	
Informed Consent and Assent 	X											
Eligibility Criteria	X											
Medical History	X											
MS-Related Medical History 	X											
Physical Examination	X											X
Body Weight	X	X		X	X	X	X		X	X	X	X
Height	X			X		X			X		X	X
Vital Signs 	X	X		X	X	X			X	X	X	X
12-Lead ECG	X										X	X
Hematology	X	X		X	X	X			X	X	X	X
Blood Chemistry	X	X		X	X	X			X		X	X
Urine Pregnancy Test 	X	X		X	X	X			X	X	X	X
Urinalysis 	X	X		X	X	X			X		X	X
PTH and Vitamin D Levels	X					X					X	X
Brain MRI Scan 	X		X	X				X	X			
EDSS	X	X		X	X	X			X		X	
Dispense Study Treatment 	X	X		X	X	X	X		X	X		
Concomitant Therapy and Procedures Recording	Monitor and record throughout the study											
AE/SAE Reporting	Monitor and record throughout the study											

AE = adverse event; ECG = electrocardiogram; EDSS = Expanded Disability Status Scale; MRI = magnetic resonance imaging; MS = multiple sclerosis;  
PTH = parathyroid hormone; SAE = serious adverse event.

 Tests and assessments must be completed prior to study treatment dispensation.

 The Final Study Visit for Study 109MS202 will serve as the Baseline Visit for this extension study. The Final Study Visit from Study 109MS202 can be within 4 weeks of the Baseline Visit for Study 109MS311 if the 2 visits cannot be combined.

 Written informed consent from the subject's parents or legal guardians and assent from the subject, if appropriate, must be obtained prior to performing any study-related procedures.

 MS-related medical history will include complete MS history of disease, MS diagnostic criteria, MS signs and symptoms, and MS treatment history.

 Vital signs include body temperature, pulse rate, and systolic/diastolic blood pressure measurements.

 For females of child bearing potential. Results must be known prior to study treatment dispensation.

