## **5 SAMPLE SIZE JUSTIFICATION**

Because this study is an extension study, the sample size was determined by the number of eligible subjects who completed Study 109MS202.

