### **6.1.7 Visit Windows**

If a subject withdraws after receiving at least one dose of BG00012, but prior to the Week 96 scheduled visit, data from the early withdrawal visit will be assigned as the next scheduled visit if it has occurred within a visit window. Scheduled visits have a window of  $\pm 5$  days.

If more than one observation is within the same window, data closest to the target regular scheduled visit will be used in the summary statistics. If more than one observation falls in the same distance from the target regular scheduled visit day, the later observation will be used in the summary statistics.

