### **6.3.2.3 Clinical Laboratory Data**

The following clinical laboratory parameters are assessed per the protocol:

- Hematology: hemoglobin, hematocrit, red blood cell count, WBC count (with differential) and platelet count.
- Blood chemistry: albumin, sodium, potassium, chloride, total bilirubin, alkaline phosphatase, ALT, AST, GGT, blood urea nitrogen, creatinine, bicarbonate, calcium, magnesium, phosphate, uric acid, and glucose
- Vitamin D and PTH (Day 1 and Week 96 only)
- Urine and serum pregnancy tests

Each laboratory value for each subject will be flagged as ‘low’, ‘normal’, or ‘high’, relative to the parameter’s normal range. Each subject’s urinalysis values will be flagged as “positive”, “negative”, or if no value is available, “unknown”.

Shifts from baseline to post baseline (Week 4/early withdrawal) high/low status for all hematology and blood chemistry parameters, and shifts from baseline to high/positive status for urinalysis will be presented.

Summary statistics will also be provided for all absolute laboratory values as well as change from baseline. The summaries for laboratory data will be data from baseline to each time point, including early withdrawal. Graphs showing the mean or change from baseline values may be presented as well.

In addition to lymphocyte count data summarized at each timepoint on study treatment, lymphocyte count over time post-treatment and the time to recovery will be descriptively summarized for subjects who develop decreases in lymphocyte count (<LLN).

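### The hematology and blood chemistry shift tables are tied to a Week 4 visit that the study does not have

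*SAP*

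**What the plan says.** SAP 6.3.2.3 (Clinical Laboratory Data) plans "Shifts from baseline to post baseline (Week 4/early withdrawal) high/low status for all hematology and blood chemistry parameters". The same sentence adds urinalysis shifts but gives them no time point. The next paragraph turns to absolute values and changes from baseline, and says "The summaries for laboratory data will be data from baseline to each time point, including early withdrawal".

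SAP Table 1 has no Week 4 column; the heading of its first post-baseline column begins "Visit 1 (Week 12±5d". Table 1 of protocol version 3.0 also starts at Week 12.

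Protocol 16.5.1.2 says that hematology, chemistry and urinalysis "will be summarized using the incidence of shifts outside the normal range", and names no week.

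Three further passages affect who would be counted:

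- Footnote 2 to protocol Table 2 covers two different events with one visit: "Discontinuation refers to discontinuation of study treatment. Withdrawal refers to withdrawal of subjects from the study".
- Protocol 10.1 adds: "Subjects who discontinue treatment may remain in the study and continue protocol-required tests and assessments".
- SAP 6.1.7 says that "data from the early withdrawal visit will be assigned as the next scheduled visit if it has occurred within a visit window".

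**The concern.** The shift tables are the only planned output that counts, analyte by analyte, how many subjects moved from normal to low or high. By-visit means and mean changes do not give that count. The AE tables do not replace it either: Protocol 15.1.1 says abnormal laboratory values are not usually treated as AEs, and Protocol Table 3 requires an AE record only when an abnormality persists. Lymphocytes have their own summary. White cell count, ALT, AST and creatinine, the blood analytes in Protocol Table 3, have no other planned count of subjects who shifted.

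If the post-baseline point names a visit that does not exist, the tables fall back on the early-withdrawal half of the parenthesis. They would then describe mainly subjects who left or stopped, who may differ from those who stayed on treatment. In a study whose primary objective is long-term safety, such tables could be misread as the shift incidence of the whole treated group.

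**Working it through.** The plan gives no figure to reproduce here. The check is a count of scheduled draws and a comparison of visit windows.

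**Step 1. Scheduled draws after baseline**, read from Table 1 of each schedule (FU = Safety Follow-Up Visit):

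| Schedule | Hematology (weeks) | n | Chemistry (weeks) | n | Draws at Week 4 |
|---|---|---|---|---|---|
| SAP Table 1 | 12, 24, 36, 48, 72, 84, 96, FU | 8 | 12, 24, 36, 48, 72, 96, FU | 7 | 0 |
| Protocol 3.0 | 12, 24, 36, 48, 60, 72, 84, 96, FU | 9 | 12, 24, 36, 48, 72, 96, FU | 7 | 0 |
| Protocol 2.0 (superseded) | as SAP | 8 | as SAP | 7 | 0 |
| Protocol 1.0 (superseded) | 16, 24, 36, 48, 64, 72, 84, 96, FU | 9 | 16, 24, 36, 48, 72, 96, FU | 7 | 0 |

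The superseded versions show only that Week 4 is not left over from an earlier schedule of this protocol.

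**Step 2. Could a scheduled visit fall into a Week 4 window?** Apply the ±5 days of SAP 6.1.7 to an imagined Week 4 visit: 28 ± 5 = days 23 to 33. The earliest real window is Week 12: 84 ± 5 = days 79 to 89. The gap is 79 − 33 = 46 days. None of the 10 numbered visits overlaps.

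**Step 3. What if Week 4 means the follow-up visit 4 weeks after the last treatment visit (Protocol 7.2.3)?** Then 1 of 8 (SAP) or 1 of 9 (version 3.0) hematology draws and 1 of 7 chemistry draws qualify. The on-treatment draws are still 0 of 7 or 0 of 8 for hematology and 0 of 6 for chemistry.

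**Step 4. What is left?**

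- *Early-withdrawal results.* The Discontinuation/Withdrawal Visit includes hematology and chemistry. SAP 6.1.7 moves such a result to a scheduled visit when it lies in that visit's window, and that visit is never Week 4. The SAP does not say whether the result still counts as early withdrawal in the shift table.
- *Tests outside Table 1 that fall near Week 4 by chance.* These are rechecks of abnormal values, 4-weekly hematology for subjects with lymphocytes below the lower limit of normal, and relapse visits.

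**Step 5. Share of subjects affected.** The documents give no discontinuation rate and no subject number: "the sample size was determined by the number of eligible subjects who completed Study 109MS202". Let d be the assumed share of treated subjects with a discontinuation/withdrawal visit. The share with no visit result in either table is 1 − d:

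| d (assumed) | 1 − d |
|---|---|
| 0.10 | 0.90 |
| 0.20 | 0.80 |
| 0.40 | 0.60 |

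Off-schedule tests near Week 4 would lower these shares by an unknown amount.

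**The case against.** **The tables would not be empty.** Withdrawal-visit results enter, and the protocol requires 4-weekly hematology for subjects with low lymphocytes, some of whom could have a draw near Week 4. This stands. It does not help subjects with normal results who complete the study, and the 4-weekly requirement covers no chemistry.

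**The sentence on each time point could cover shifts too.** Its subject is laboratory summaries in general, and it also mentions early withdrawal. But it follows the sentence on absolute values and changes, and applying it to shifts would contradict the explicit parenthesis. The text would still need correcting.

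**Early withdrawal is clearer than it looks.** Protocol 7.2.3 ties the Early Withdrawal Visit to leaving the study, and SAP 6.3.2.2 reports study withdrawal and treatment discontinuation separately. This has force. If the term means study withdrawal only, however, subjects who stop treatment and stay in the study also drop out of the tables.

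**A programmer would catch it, and the analysis is only descriptive.** Probably, and every value is flagged low, normal or high, so correct tables can be built from the same data. But the reasonable repairs give different counts. The study is open-label with periodic data summaries (Protocol 16.7, SAP 4), so without SAP wording the choice could be made after results are seen.

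**The protocol sets no period.** True: Protocol 16.5.1.2 does not say that shifts are counted over all 96 weeks. It equally gives no basis for a Week 4 limit.

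**Conclusion.** The point holds. As written, scheduled post-baseline draws contribute nothing to the hematology and chemistry shift tables: 0 of 8 (SAP schedule) or 0 of 9 (protocol 3.0) for hematology, and 0 of 7 for chemistry. These counts rest only on the published schedules. The 60% to 90% of subjects with no visit result rests on assumed discontinuation rates of 40% down to 10% and is illustrative.

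The damage is confined to these two tables. Not affected are the AE-based primary endpoint, urinalysis shifts, low/normal/high flags, by-visit values and changes, and the lymphocyte summaries. Week 4 may be text carried over from another plan, since the SAP's abbreviation list contains vaccine terms this study does not use, but that is inference. The wording should be corrected, although it does not threaten the study's main conclusions.

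**What to change.** Delete the parenthesis in SAP 6.3.2.3 and define the post-baseline point in one of two ways:

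1. Baseline to any low value and, separately, to any high value after the first dose in 109MS311. This is closest to the incidence that Protocol 16.5.1.2 plans.
2. Baseline to each scheduled post-baseline visit plus the discontinuation/withdrawal visit. This is well defined, but it answers a per-visit question and does not give the number of subjects who ever shifted.

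With either option, also state:

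- whether unscheduled results count, because Protocol 11.2.1 has abnormal values retested more often, which gives those subjects more chances to show a shift;
- that results after the last dose are identified separately, because Protocol 11.6 allows commercial BG00012 during follow-up;
- whether early withdrawal means leaving the study, stopping treatment, or both, and how a result relabelled under SAP 6.1.7 enters the table.

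The cost is SAP wording and table shells. No extra sampling is needed.

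Two small alignments can be made in the same edit, though neither is part of this defect. SAP 6.3.2.3 limits vitamin D and PTH to Day 1 and Week 96, while SAP Table 1 also lists Week 48 and the Safety Follow-Up Visit, and SAP Table 2 lists the discontinuation visit. In the Week 60 column, SAP Table 1 lacks the hematology and vital signs that protocol 3.0 has, and shows a body weight that protocol 3.0 does not.

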**Table 2: Additional Study Activities for Study 109MS311**

Tests and Assessments	Unscheduled Relapse Assessment Visit  (within 72 hours after symptom onset)	Discontinuation/ Withdrawal Visit  (as soon as possible but no later than 4 weeks after last dose of study treatment)	Lymphocyte Follow-Up Visit 
Physical Examination	X	X	X
Body Weight	X	X	X
Height		X	
Vital Signs 	X	X	X
12-Lead ECG		X	
Hematology 	X	X	X
Blood Chemistry 	X	X	
Urine Pregnancy Test 	X	X	
Urinalysis 	X	X	
PTH and Vitamin D Levels		X	
EDSS	X	X	
Brain MRI Scan 		X 	
Relapse Assessment	X		
Concomitant Therapy and Procedures		Monitor and record throughout the study	
AE/SAE Recording		Monitor and record throughout the study	

AE = adverse event; ECG = electrocardiogram; EDSS = Expanded Disability Status Scale; LLN = lower limit of normal; MRI = magnetic resonance imaging; PTH = parathyroid hormone; SAE = serious adverse event.

 An Unscheduled Relapse Assessment Visit will be conducted within 72 hours of symptom onset of a suspected relapse (i.e., new or recurrent neurologic symptom[s]).

 Discontinuation refers to discontinuation of study treatment. Withdrawal refers to withdrawal of subjects from the study. The Discontinuation/Withdrawal Visit should be conducted as soon as possible and no later than 4 weeks after the last dose of study treatment.

 Subjects who complete, temporarily withhold, or permanently discontinue study treatment for any reason and have a lymphocyte count <LLN will continue protocol-required visits and assessments and be followed every 4 weeks for 24 weeks and then every 3 months (unless clinically indicated more often or at the Investigator's discretion) until the lymphocyte count is  $\geq$ LLN or for 52 weeks after the last dose (whichever is sooner).

 Vital signs include body temperature, pulse rate, and systolic/diastolic blood pressure measurements.

 Hematology testing must be performed every 4 weeks in subjects with lymphocyte count <LLN

 Study treatment must be temporarily withheld or permanently discontinued if any of the laboratory values meet the criteria defined in the protocol.

 For females of childbearing potential.

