#### **6.3.2.1 Definition of Baseline Value and Visit Windows**

Baseline values and visit windows for safety summaries are defined in the same way as they are for efficacy analyses (see Section 6.1.1 and 6.1.7, respectively).

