#### **6.3.2.4 Vital Signs Data**

The analysis of vital signs will focus on the incidence of clinically relevant abnormalities. The number of subjects evaluated and the number and percentage of subjects with clinically relevant post-baseline abnormalities will be presented. The criteria for clinically relevant post-baseline abnormalities are shown in the following table (Table 2). Summary statistics for actual values and change from baseline will also be presented.

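### The SAP sets its hematology and chemistry shift at a Week 4 visit that does not exist, so as written it uses no scheduled on-treatment draw from subjects who complete treatment

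*SAP*

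**What the plan says.** SAP 6.3.2.3 states one shift analysis for blood results: "Shifts from baseline to post baseline (Week 4/early withdrawal) high/low status for all hematology and blood chemistry parameters". The urinalysis shift in the same sentence carries no time point.

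The SAP's own Table 1 goes from Day 1 directly to "Visit 1 (Week 12±5d"), and so does Table 1 of protocol v3.0. Early withdrawal is a real visit with hematology and chemistry: "The Discontinuation/Withdrawal Visit should be conducted as soon as possible" (SAP Table 2).

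The remaining laboratory summaries are by visit: "The summaries for laboratory data will be data from baseline to each time point, including early withdrawal". On-treatment lymphocytes are also summarized by time point. The separate summary for subjects who fall below LLN covers counts after treatment and time to recovery. SAP 6.1.7 gives scheduled visits a window of ±5 days and, where several values share a window, says that "data closest to the target regular scheduled visit will be used in the summary statistics". SAP 6.3.2.1 applies this to safety: "Baseline values and visit windows for safety summaries are defined in the same way as they are for efficacy analyses".

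Protocol 16.5.1.2 commits to summarizing how often laboratory values move out of the normal range, with no time point attached.

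**The concern.** A shift table tied to a visit that nobody attends has no scheduled data for completers. Its only reliably populated part is early withdrawal, so it would describe a selected subset.

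The by-visit summaries do not fill the gap. They give n, mean, standard deviation, median and range (SAP 6), so a very low count at a visit appears only as the minimum of a range, with no number of subjects below a threshold. The SAP prepares for more than this, since "Each laboratory value for each subject will be flagged as" low, normal or high. For vital signs it already plans subject-level incidence: "the number and percentage of subjects with clinically relevant post-baseline abnormalities will be presented".

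Long-term safety is the primary objective. Protocol 5.3.2 links progressive multifocal leukoencephalopathy to lymphopenia that is both deep and lasting, and Table 5 makes more than 6 months below 500/mm³ a mandatory stop. How many subjects reached that level is therefore a key laboratory result. AE tables are not a dependable substitute. Protocol 15.1.1 leaves it to the Investigator whether a laboratory value is an AE, and Tables 4 and 5 do not require one for lymphocytes, whereas Table 3 does for persistent abnormalities in other analytes.

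**Working it through.** The plan states no figure to reproduce here; the check is of schedules and counts.

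**1. Does any visit fall at Week 4?** Week 4 is Day 28. The Week 12 window opens at 7 × 12 − 5 = Day 79, which is 79 − 28 = 51 days later. Day 28 lies in no window.

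**2. Scheduled on-treatment draws (protocol v3.0 Table 1).** Hematology: Weeks 12, 24, 36, 48, 60, 72, 84, 96 = 8. Chemistry: Weeks 12, 24, 36, 48, 72, 96 = 6. None is at Week 4, so a completer contributes 0 of 8 and 0 of 6. The SAP schedule omits hematology at Week 60, which leaves 7.

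**3. Could unscheduled tests fill Week 4?** Only incidentally. Protocol 8.2 excludes lymphocytes below 500/mm³, so a subject can enter between 500/mm³ and LLN and be retested near Day 28, but that subject is already low at baseline. A subject normal at baseline has no scheduled draw before Week 12. Apart from a chance relapse visit, a normal-to-low shift cannot appear.

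**4. Could Week 4 mean the Safety Follow-Up Visit?** That visit falls up to 4 weeks after the last dose (SAP 2.2). It supplies one value after study treatment and still ignores every on-treatment draw.

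**5. How many lymphocyte counts lie between visits?** Take a subject below LLN from Week 12 to Week 96, tested every 4 weeks (protocol Table 4; Table 2 footnote 5): Weeks 16, 20, …, 96 = 21 counts.
- Windows at hematology visits only: 7 inside (Weeks 24, 36, 48, 60, 72, 84, 96), 14 outside.
- Windows at all scheduled visits, adding Weeks 16 and 64: 9 inside, 12 outside.
- If the 3-monthly step-down in protocol 11.2.1 applies on treatment (3 months taken as 12 weeks): Weeks 16, 20, 24, 28, 32, 36, 48, 60, 72, 84, 96 = 11 counts. Outside are 16, 20, 28, 32 = 4, or 3 if the Week 16 window is used.

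**6. Which dips below 500/mm³ are seen only off schedule?** Assume a dip of D weeks that starts at random relative to visits, in a subject on 4-weekly testing. The probability that it contains a 4-weekly draw is min(1, D/4).
- Hematology visits only: the probability that it contains a scheduled draw is min(1, D/12). The share caught only off schedule is 1 − min(1, D/12)/min(1, D/4).
- All scheduled visits: gaps over 48 weeks are 12, 4, 8, 12 and 12. For D ≥ 4 the share is Σ max(0, gap − D)/48. For D < 4 it is 1 − (5D/48)/(D/4) = 7/12.

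| Dip length | Hematology visits only | All scheduled visits |
|---|---|---|
| up to 4 weeks | 67% | 28/48 = 58% |
| 6 weeks | 50% | 20/48 = 42% |
| 8 weeks | 33% | 12/48 = 25% |
| 10 weeks | 17% | 6/48 = 12.5% |
| 12 weeks or more | 0% | 0% |

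With ±5-day jitter on every draw, simulation of the first column gives 65% at 4 weeks and 2% at 12. Under the step-down, these shares hold for the first 24 weeks of retesting only.

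**The case against.** The strongest reply is that Week 4 is a clerical slip. A programmer cannot execute it and would have to ask. The urinalysis shift and protocol 16.5.1.2 are both untimed. The SAP abbreviation list also carries vaccine terms that the supplied text never uses, which suggests, without proving, text carried over from elsewhere. On this view the intended table would be sensible and nothing would be lost. That may be how it ends, but the SAP does not say which value replaces Week 4. Visit by visit, last value and worst value give different tables, so the choice needs to be written down.

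Three further points stand as limits:

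- A reader might infer that lasting lymphopenia would go unseen. The documents do not support that. Under protocol v3.0, episodes of 12 weeks or more meet a scheduled draw. Stopping decisions use each subject's own counts, not these tables, and an IDMC reviews interim safety data.
- A reader might infer that the SAP discards out-of-window results, or that only the shift relies on low status. The SAP never excludes such results expressly; that follows by inference from by-visit summaries and the window rule. The post-treatment recovery summary also needs to know who fell below LLN.
- Counting subjects below a threshold adds to a descriptive single-arm plan. It is an improvement, separate from the error.

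**Conclusion.** The shift time point is wrong as written and should be corrected. Taken literally, it gives completers no scheduled on-treatment blood result in the shift, and the one charitable reading does not repair that. This part rests on the two schedules alone.

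The lymphocyte count by threshold is a cheap addition. Its case rests on 12 to 14 of 21 counts (3 to 4 of 11 with step-down) falling outside visit windows, and on about 58% to 67% of detected dips of up to 4 weeks being seen only off schedule. Both ranges depend on whether the Week 16 and 64 windows are used for laboratory values. The dip shares also assume random timing.

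These are shares of draws and of detected dips, in subjects already known to be below LLN. The documents give no frequency of such dips, so no number of affected subjects follows. A low episode lying wholly between draws in a subject not on extra testing cannot be recovered by any SAP wording. Nor do the figures show a loss of information on duration, since the SAP plans no on-treatment duration analysis from any set of draws.

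**What to change.** In SAP 6.3.2.3:

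- Replace the Week 4/early withdrawal time point with a shift from baseline to the worst on-treatment value: the lowest for lymphocytes and WBC, and the clinically adverse direction for chemistry. Use all scheduled and unscheduled central-laboratory results, and define the on-treatment period.
- Report the number and percentage of subjects with lymphocytes below LLN and below 500/mm³ at any time on treatment, with a second row for below 500/mm³ confirmed on retest.
- Keep the by-visit tables on windowed values and add Week 60 hematology to match protocol v3.0.
- Optionally, list the duration of each episode below 500/mm³.

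The cost is SAP wording, one worst-value variable per analyte and one confirmation flag; no new data are collected. The downside is that subjects tested more often have more chances to show a low value. A footnote should say so, and the confirmed row limits the effect.
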